1.2 Study objectives and endpoints

The primary objective of this study is to assess the effect of in hospital initiation of sacubitril/valsartan vs. enalapril on the time-averaged proportional change of N-terminal prohormone of B-type natriuretic peptide (NT-proBNP) from baseline in patients who have been stabilized following hospitalization for ADHF and reduced ejection fraction (left ventricular ejection fraction [LVEF] $\leq 40\%$). Weeks 4 and 8 will be included in the analysis (primary analysis time point).

The secondary objectives of this study are to examine the effect of sacubitril/valsartan vs. enalapril on:

- The proportional change in NT-proBNP from baseline to Week 8
- Incidence of symptomatic hypotension during 8 weeks of treatment
- Incidence of hyperkalemia (Potassium > 5.5 mEq/L) during 8 weeks of treatment
- Incidence of angioedema during 8 weeks of treatment
- Biomarkers: hs-Troponin (high sensitivity), urinary cyclic Guanosine 3',5'-Monophosphate (cGMP) and B-type natriuretic peptide (BNP) to NT-proBNP ratio at 4 and 8 weeks

2 Statistical methods

2.1 Data analysis general information

, a Novartis-designated Contract Research Organization (CRO) will be performing all analyses outlined in this SAP. SAS[®] version 9.3 (or higher) will be used for all analyses.

Data from all centers that participate in this protocol will be combined, so that an adequate number of patients will be available for analysis.

Unless otherwise specified, for continuous data, the mean, standard deviation, median, first and third quartile, interquartile range, and minimum and maximum values will be presented. For categorical data, frequencies and percentages will be presented. All statistical tests will be conducted against a two-sided alternative hypothesis, employing a significance level of 0.05.

All data will be provided in listings in addition to summaries described below.

2.1.1 General definitions

Study treatment

Patients will receive either sacubitril/valsartan or enalapril during the first 8 weeks of the study. Study treatment will refer to either of these two drugs.

Baseline

For safety labs and biomarkers, baseline is defined as the last non-missing assessment collected <3 hours from the first dose of study treatment, including matching placebos. For patients not treated, baseline is defined as the last non-missing assessment prior to or on the date of randomization. BNP and NT-proBNP values will be based on clinical laboratory samples processed and assessed by the central laboratory.

For other assessments, including those for which assessment time is collected (ECGs, HF Signs and Symptoms, and pregnancy tests), baseline is defined as the last non-missing assessment prior to or on the start date of study treatment (randomization date for patients not treated), including matching placebos.

Date of first administration of study treatment

Double-blind phase: The date of first administration of study treatment in the double-blind phase is defined as the first date a dose of study treatment is administered and recorded on the Dose Administration (Visit 2) electronic case report form (eCRF).

Open-label phase: The date of first administration of study treatment in the open-label phase is defined as the first date a dose of sacubitril/valsartan is administered in the open-label phase and recorded on the Dose Administration (Visit 7) eCRF.

Pooled phase: The date of first administration of study treatment in the pooled phase is defined as the first date a dose of sacubitril/valsartan is administered either in the double-blind phase or open-label phase.

Date of last administration of study treatment

Double-blind phase: The date of last administration of study treatment in the double-blind phase is defined as the last date a dose of study treatment is administered in the double-blind phase and recorded on the Dose Administration (Visit 7) eCRF, or earlier if prematurely discontinued and recorded on the Early Investigational Product Permanent Discontinuation eCRF.

Open-label phase: The date of last administration of study treatment in the open-label phase is defined as the last date of sacubitril/valsartan is administered in the open-label phase and recorded on the Drug Administration eCRF.

Pooled phase: The date of last administration of study treatment in the pooled phase is defined as the last date of sacubitril/valsartan administered either in double-blind phase or open-label phase.

Study day

The study day describes the day of the assessment relative to the date of randomization.

The study day will be calculated as the difference between the date of assessment and the date of randomization plus 1. If the date of assessment is prior to the date of randomization, the study day will be negative and will be calculated as the difference between the date of the assessment and the date of randomization.

Double-blind phase

Assessments performed at Weeks 1, 2, 4, 6, or 8 (including, but not limited to, vital signs) are assigned to the double-blind phase for summarization purposes. Unscheduled assessments are not assigned to a study phase for purposes of by-visit summaries.

For summarization of adverse events [AEs], medications, protocol deviations, notable vital signs and laboratory abnormalities, and symptomatic hypotension by study phase, an assessment during the double-blind phase is defined as any assessment obtained in the following time interval:

Date of randomization (or date of first administration of study treatment, as appropriate) through the date of the Week 8 visit, inclusive. For patients without a Week 8 visit, a projected Week 8 visit date will be derived relative to their randomization date.

An 'active treatment' assessment is defined for sensitivity analyses starting with the first dose of study treatment in patients randomized to enalapril and the third dose of study treatment in patients randomized to sacubitril/valsartan.

Open-label phase

Assessments performed at Weeks 10 or 12 (including, but not limited to, vital signs) are assigned to the open-label phase for summarization purposes. Unscheduled assessments are not assigned to a study phase for purposes of by-visit summaries.

For summarization of AEs, medications, protocol deviations, notable vital signs and laboratory abnormalities, and symptomatic hypotension by study phase, an assessment during the open-label phase is defined as any assessment obtained in the following time interval:

After the date of the Week 8 visit. For patients without a Week 8 visit, a projected Week 8 visit date will be derived relative to their randomization date.

Patients who died, withdrew consent, or were lost to follow-up prior to or on their projected Week 8 visit date will be excluded from the open-label phase.

Pooled phase

An assessment during the pooled phase is defined as any assessment obtained in the doubleblind phase for patients randomized to sacubitril/valsartan, or any assessment obtained in the open-label phase regardless of randomized treatment arm.

Last contact

The date of last contact will be determined from the Date of Last Contact field on the Study Completion/Exit eCRF.

Year, month and week

For reporting purposes, the rules below will be followed to convert a year, month and week to days.

1 year = 365.25 days

1 month = 30.3475 days

1 week = 7 days

1 day = 24 hours

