3.1 Study design

This study will use a randomized, double-blind, double-dummy, active-controlled, parallel group design. Eligible patients hospitalized for ADHF will be randomized no earlier than 24 hours and up to ten days of presentation while still hospitalized.

At the time of randomization, patients will have been stabilized, defined for this study as:

- SBP ≥100mm Hg for the preceding 6 hours prior to randomization; no symptomatic hypotension
- No increase (intensification) in i.v. diuretic dose within last 6 hours prior to randomization
- No i.v. inotropic drugs for 24 hours prior to randomization
- No i.v. vasodilators including nitrates within last 6 hours prior to randomization

All patients will need to meet all other inclusion and none of the exclusion criteria.

In order to provide for a necessary 36 hour washout of prior ACEi treatment prior to receiving sacubitril/valsartan (known as LCZ696 in prior trials), the supplied blinded study drug for those allocated to sacubitril/valsartan will be placebo only until the 3rd dose. Because the study is blinded, ALL patients, regardless of randomization arm, need to remain in the hospital for six hours after they have received their 3 rd dose of study medication. Please see Figure 3-2.

Patients will be randomized to sacubitril/valsartan or enalapril. Initial dose will be determined by the blood pressure at the time of randomization. Study treatment will be titrated t o the Level #3 target doses of sacubitril/valsartan 97/103 mg bid and enalapril 10 mg bid. Titration will be based on blood pressure at the time of the visit. Dose adjustments will only be allowed if indicated per protocol defined safety and tolerability criteria and investigator judgement.

At the end of the 8-week treatment period ALL patients will need to have a 36 hour washout from study treatment prior to starting the open label extension to ensure that the blinding of the core study is maintained. To facilitate this washout, patients should take their final dose of study drug on the morning of their week 8 visit and then begin open label sacubitril/valsartan after 36 hours in the evening of week 8 visit + one day.

All patients will start open label treatment on sacubitril/valsartan at their final dosing level during double blind treatment. However, at an investigator's judgement, starting dose may be adjusted by one dose level up or down.

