4 Weeks (Visit 5)	1	<100	1
	1	≥100	2
	2	<100	2
	2	≥100	3
6 Weeks (Visit 6)	1	<100	1
	1	≥100	2
	2	<100	2
	2	≥100	3

**Up titration may be done prior to the week 1 visit for patients who were started at dose level 1 who were previously on high dose RAS blockade (>10 mg enalapril total daily dose or > 160 mg valsartan total daily dose or equivalent doses of other ACEi or ARB).

Confidential

Dose adjustments to lower dose levels may be made at any time at both scheduled and unscheduled visits only if indicated for blood pressure control/tolerability reasons.

Study medication should be taken with a glass of water with or without food. If the patient misses taking any study drug dose, he/she should take it as soon as possible, unless it is almost time for the following scheduled dose. In this case, the patient should skip the missed dose and return back to his/her regular study drug administration schedule.

All dosage prescribed and dispensed to the patient and all dose changes during the study must be recorded in the IWRS and on the Dosage Administration Record eCRF.

The investigator should promote compliance by instructing the patient to take the study treatment exactly as prescribed and by stating that compliance is necessary for the patient's safety and the validity of the study. The patient should be instructed to contact the investigator if he/she is unable to take the study treatment as prescribed for any reason.

All patients that complete 8 weeks of treatment will proceed with a 4 -week follow up on open-label sacubitril/valsartan. All patients will have the wash out in order to maintain the blinding of the core study. To facilitate this washout, patients should take their final dose of study drug on the morning of their week 8 visit and then begin open label sacubitril/valsartan after 36 hours in the evening of week 8 visit + one day. All patients will start open label treatment on sacubitril/valsartan at their final dosing level during double blind treatment. However, at an investigator's judgement, starting dose may be adjusted by one dose level up or down.

The intent of the open-label phase is to have the patients up-titrated to the desired dose level #3 (200 mg sacubitril/valsartan) based on clinical need and investigator judgement.

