2.2 Analysis sets

The following analysis data sets will be used in the analyses:

Randomized Set (RS): The RS will consist of all randomized patients.

Full Analysis Set (FAS): The FAS will consist of all randomized patients with the exception for those patients who have not been qualified for randomization and have not received study treatment, but have been inadvertently randomized into the study. Following the intent-to-treat principle, patients will be analyzed according to the treatment to which they were assigned at randomization. Efficacy variables will be analyzed based on the FAS as the primary set.

Safety Set (SS): The SS will consist of all randomized patients who have received at least one dose of study treatment. Patients will be included in the analysis according to the treatment actually received. The SS will be used for the analyses of safety variables.

Per-Protocol Set (PPS): The PPS will be a subset of the FAS, which will consist of the patients who do not have major deviations from the protocol procedures. Major protocol deviations will be pre-specified prior to unblinding treatment code for analysis. This supplemental analysis set will be used to support the primary analysis results.

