2.8.1.2 General rules for AE reporting

AE summaries will include all treatment-emergent AEs (TEAEs). TEAEs are defined as AEs starting on or after the first day of study treatment. All AEs will be listed. AEs starting prior to the first day of study treatment (non-TEAEs) will be flagged in the listings.

All TEAEs will be summarized by study phase as defined in Section 2.1.1.

TEAEs will be summarized by presenting the number and percentage of patients having at least one TEAE, having at least one TEAE in each primary SOC, and for each PT using MedDRA coding. A patient with multiple occurrences of a TEAE will be counted only once in the AE category.

Separate summaries will be presented by SOC, PT and severity. A patient with multiple severities for an AE will be summarized under the worst severity recorded for the event.

Any information collected will be listed as appropriate.

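### The open-label and pooled sacubitril/valsartan safety phases carry no dosing condition, so they count patients who stay in follow-up without open-label drug, including enalapril patients never exposed to sacubitril/valsartan

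*SAP*

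**What the plan says.** SAP 2.1.1 uses two rules for study phases. By-visit summaries go by visit label (Weeks 10 and 12 are open-label). Summaries by interval go by calendar date, and there the open-label phase is any assessment obtained "After the date of the Week 8 visit. For patients without a Week 8 visit, a projected Week 8 visit date will be derived" from the randomization date. The only exclusion is: "Patients who died, withdrew consent, or were lost to follow-up prior to or on their projected Week 8 visit date will be excluded" from the phase. The pooled phase joins the double-blind assessments of the sacubitril/valsartan arm with "any assessment obtained in the open-label phase regardless of randomized treatment arm".

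Other passages decide who falls inside these windows:

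- Protocol 5.5.8 asks patients who stop study drug to stay in the trial and keep attending visits.
- Protocol 5.5.4 links open-label drug to finishing treatment: "All patients that complete 8 weeks of treatment will proceed" to it.
- SAP 2.2 admits a patient to the Safety Set after one dose of study treatment, which may be enalapril. SAP 5.6, Table 2 removes only patients with no double-blind treatment. No open-label safety set is defined.
- SAP 2.8.1.2 says "TEAEs are defined as AEs starting on or after the first day of study treatment", and for an enalapril patient that first day is an enalapril day.
- SAP 2.8.2 summarizes deaths by the same phases, in the FAS.
- SAP 2.4.1 computes open-label and pooled exposure from first and last dose dates.

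**The concern.** The pooled phase keeps sacubitril/valsartan double-blind time and leaves out enalapril double-blind time. That selection makes sense only as a summary of experience on sacubitril/valsartan, and SAP 2.3.1 and 2.4.2 label the columns that way. Yet after Week 8 a patient enters by being in follow-up, whether or not the drug was taken.

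The numerator and denominator then describe a different group from the exposure reported beside them. Patients who stopped early are also not a random sample: some stopped because of adverse events, and Protocol 5.5.6 lets them take a non-study ACE inhibitor or ARB once study drug is off. An event on such a drug after Week 8 could appear in a pooled sacubitril/valsartan table. SAP 2.2 states the principle "Patients will be included in the analysis according to the treatment actually received". That sentence governs set membership and arm rather than time windows, but these tables do not meet its purpose.

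**Working it through.** There is no stated figure to reproduce, since the point concerns a definition. I followed patients through the rules using the calendar in Protocol Table 6-1 (Week 8 = day 56, Week 12 = day 84).

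**1. An enalapril patient who stops early, stays in follow-up and never starts open-label drug**

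| Step | Rule | Result |
|---|---|---|
| Safety Set | one double-blind dose (SAP 2.2; 5.6, Table 2) | included |
| Open-label exclusion | died, withdrew or lost by projected Week 8 (SAP 2.1.1) | not excluded |
| Treatment-emergent | onset on or after first study treatment (SAP 2.8.1.2) | yes |
| Open-label phase | after actual or projected Week 8 (SAP 2.1.1) | included from day 57 |
| Pooled phase | open-label phase, either arm (SAP 2.1.1) | included |
| Sacubitril/valsartan exposure | first to last dose (SAP 2.4.1) | 0 days |

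If the last enalapril dose was on day 7, events on days 57 to 84 lie 57 − 7 = 50 to 84 − 7 = 77 days after it. If it was on day 28, they lie 29 to 56 days after it. For deaths, the FAS can also include a patient who took no study drug.

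**2. Share of the pooled set (illustration)**

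The documents give no count of patients who never start open-label drug. Assume 10% to 25% of the enalapril arm, all still in follow-up after projected Week 8:

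- 882 / 2 = 441 enalapril patients.
- 441 × 0.10 = 44 and 441 × 0.25 = 110.
- 44 / 882 = 5.0% and 110 / 882 = 12.5%.

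The 882 is a round figure. Enalapril patients who died, withdrew or were lost by projected Week 8 leave the pooled set.

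**3. Direction of the bias**

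With unexposed share f, incidence p among the exposed and q among the unexposed, the table shows p(1 − f) + qf. Take p = 10% (assumption):

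| | f = 5% | f = 12.5% |
|---|---|---|
| q = 0 | 9.5% | 8.75% |
| q = 2p = 20% | 9.5% + 1.0% = 10.5% | 8.75% + 2.5% = 11.25% |

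The reported figure is too low if non-starters have few events and too high if they are sicker.

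**4. Washout**

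The protocol has patients take the last double-blind dose on the morning of Week 8 and "begin open label sacubitril/valsartan after 36 hours in the evening of week 8 visit + one day". The phase opens at 00:00 on day 57. With a morning dose between 06:00 and 11:00 (assumption), the first open-label dose falls between 18:00 and 23:00 on day 57, so 18 to 23 washout hours lie inside the phase. That is under one calendar day for a patient on schedule.

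**The case against.** The strongest reply is that this was a choice. SAP Amendment 1 removed on-treatment wording and the 28-day lag, and renamed treatment phases as study phases. A study-phase summary is a recognised alternative. This is a fair defence of not having an end-of-window lag, on which statisticians differ. It does not cover the pooled phase, which is built by drug and labelled by drug.

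A second reply is that the Protocol summary and Protocol 3.1 speak of all patients moving to open-label drug. Any who did are rightly counted. The gap concerns those who did not, and nothing in SAP 2.1.1 removes them.

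A third reply also has force. SAP 2.8.4.6 summarizes angioedema by timing relative to dose and by ACE inhibitor use during the trial, and lists the adjudicated result. SAP 2.4.2 lists non-study ACE inhibitor and ARB use. A single misplaced case could be found, but the table itself would still be wrong.

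A reader might go further in four ways that the documents do not support:

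- *The window is unlimited.* The definition has no end date, but collection limits it. Scheduled visits stop at day 84, the 16-week call is source documentation only, and Protocol 7.2.2 ends routine SAE reporting 30 days after participation stops.
- *The washout books much enalapril time to sacubitril/valsartan.* The overlap is under one day.
- *Rates appear at 0.75 to 0.90 of their true value.* That requires zero events in non-starters and borrows the 25% missing NT-proBNP rate, which is not a non-start rate. For the pooled set even the zero-event case gives 0.875 to 0.95.
- *One washout angioedema case would add 23%.* The sum is 0.005 × 882 = 4.4 and 1 / 4.4 = 23%, but it presupposes the case. At the cited 0.2% for enalapril, 441 × 0.002 = 0.88 events. Even if all fell within 56 days, one day expects 0.88 / 56 = 0.016.

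**Conclusion.** The point holds for who is counted. As written, the open-label and pooled sacubitril/valsartan summaries by interval include patients with no open-label dose, and among them enalapril patients with no sacubitril/valsartan exposure at all.

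The size cannot be computed from the documents. The 5% to 12.5% share rests on an assumed non-start rate of 10% to 25% among enalapril patients still in follow-up, and the sign of the bias depends on how non-starters fare. The consequence is limited to descriptive, non-randomized safety tables. The 8-week secondary safety endpoints, the randomized double-blind comparison and the primary endpoint are untouched. It should be corrected because the correction is cheap and these tables will be read as experience on the drug.

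**What to change.** In SAP 2.1.1:

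1. Limit the interval-based open-label phase, and the enalapril-randomized patients' part of the pooled phase, to patients with at least one recorded open-label dose.
2. Start the phase on the date of first open-label administration, which that section already defines from the Dose Administration (Visit 7) eCRF.
3. In a separate row under the randomized arm, show post-Week 8 events in patients with no open-label dose, and events after Week 8 but before the first open-label dose date. No event is then lost.
4. Flag events on the first open-label dose date whose timing relative to the dose is unknown. The SAP defines that dose by date, so a date rule alone cannot separate them.

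An end-of-window lag is optional.

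The cost is a short SAP change, reprogramming of the phase flags from dose dates already collected, and one extra table row. No new data or visits are needed.

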2.3 Patient disposition, demographics and other baseline characteristics

2.3.1 Patient disposition

All patients will be used for the summary of patient disposition. The following categories will be summarized:

- Number of patients who were screened
- Primary reason for not continuing to double-blind phase

- Investigator decision
- Subject/Guardian decision
- Screen failure
- Adverse event
- o Pregnancy
- Study terminated by sponsor
- Technical problems
- o Death
- Number of patients who were randomized
- Number and percentage of patients who were treated
- Number and percentage of patients who prematurely discontinued study treatment during double-blind phase
- Number and percentage of patients who prematurely discontinued study treatment during double-blind phase, excluding deaths
- Number and percentage of patients who prematurely discontinued study treatment during open-label phase
- Number and percentage of patients who prematurely discontinued study treatment during open-label phase, excluding deaths
- Reasons for premature discontinuation of study treatment (separately for double-blind phase and open-label phase)
 - o Adverse event
 - o Death
 - Protocol deviation
 - Investigator decision
 - Subject/Guardian decision
 - Lost to follow-up
 - Technical problems
 - o Pregnancy
 - Withdrawal of consent
 - Noncompliance with study treatment
 - Study terminated by sponsor
- Study duration in months [(date of last contact/death date of randomization +1)/30.3475]

A separate summary for study completion will be presented and the FAS will be used. The following categories will be summarized at Week 8 by treatment group, open-label and pooled sacubitril/valsartan:

- Patients who received at least one dose of study treatment
- Patients who did not receive at least one dose of study treatment
- Patients with known vital status at Week 8
 - Dead prior to opening of projected Week 8 visit window
 - Completed Week 8 visit after opening of projected Week 8 visit window
 - Any visit/contact with visit date after opening of projected Week 8 visit window
 - Vital status recorded with last known alive date after opening of projected Week 8 visit window
- Patients with unknown vital status at Week 8
 - Lost to follow-up prior to opening of projected Week 8 visit window
 - Withdrawal of informed consent to any follow-up prior to opening of projected Week 8 visit window

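### The SAP's open-label and pooled sacubitril/valsartan phases require no dose of the drug, so patients who never start it count in the descriptive safety tables

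*SAP*

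**What the plan says.** SAP 2.1.1 gives the open-label interval for safety summaries as "After the date of the Week 8 visit. For patients without a Week 8 visit, a projected Week 8 visit date will be derived" from the randomization date. One group is then removed: "Patients who died, withdrew consent, or were lost to follow-up prior to or on their projected Week 8 visit date will be excluded" from the phase. The pooled phase is the double-blind assessments of patients randomized to sacubitril/valsartan, "or any assessment obtained in the open-label phase regardless of randomized treatment arm".

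The same section does define a dosing start for the open-label phase, the "first date a dose of sacubitril/valsartan is administered in the open-label phase and recorded on" the Visit 7 dosing form. The phase interval does not use that date. SAP 2.4.1 uses actual dosing dates for exposure.

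These phases structure the summaries of adverse events (2.8.1.2), deaths on the FAS (2.8.2), notable laboratory values (2.8.3), and notable vital signs and symptomatic hypotension (2.8.4.2). Elsewhere (2.3.1, 2.4.1, 2.4.2) the SAP labels the corresponding groups as open-label and pooled sacubitril/valsartan.

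**The concern.** A reader of a table headed open-label or pooled sacubitril/valsartan will take it as experience in patients given that drug. The definitions do not ensure this. Stopping blinded drug, or never starting open-label drug, is not among the exclusions. The protocol expects such patients: 5.5.8 asks those who stop study drug to remain in the trial, and 5.5.6 permits them a non-study ACE inhibitor or ARB.

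At stake is the meaning of the descriptive safety counts. A patient with no sacubitril/valsartan exposure can add an event and a denominator unit to these phases while adding no days to the dose-based exposure table printed beside them.

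**Working it through.** The plan gives no figure for this point, so the check is to follow cases through the rules.

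**Case 1: an enalapril patient stops at Week 3, stays in follow-up, never takes sacubitril/valsartan, and has an event at Week 10.**
1. Analysis sets. The patient was dosed, so is in the FAS. SAP 5.6 Table 2 excludes from the Safety Set only those with no double-blind treatment, so the patient is there too.
2. Open-label phase. Week 10 is after the actual or projected Week 8 date. The patient had not died, withdrawn consent or been lost by then, so is included.
3. Pooled phase. Open-label assessments enter from either arm, so the patient is included.
4. Deaths, notable laboratory values, notable vital signs and symptomatic hypotension follow the phase rule directly, so the event counts in both phases.
5. Adverse events are unclear. "TEAEs are defined as AEs starting on or after the first day of study treatment", and "Study treatment will refer to either of these two drugs", so on the plain reading a Week 10 event counts. The phase-specific first-dose dates could be read as requiring an open-label dose, but no rule ties them to the counts.
6. Exposure (2.4.1): zero open-label and zero pooled days.

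**Case 2: a patient randomized to sacubitril/valsartan takes only the first two blinded doses.** Both are placebo (Protocol 3.6). The pooled phase takes this arm's double-blind assessments without requiring the third dose, so the patient counts there without having received the drug.

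**Does other text remove these patients?**
- The Safety Set rule is "Patients will be included in the analysis according to the treatment actually received". It sets no denominator for either phase and does not govern deaths, which use the FAS.
- The completion table in 2.3.1 has a row for "Patients who did not receive at least one dose of study treatment". Study treatment means either drug, so the Case 1 patient is not in that row.
- Post-randomization non-study ACE inhibitor or ARB use is only listed (2.4.2).

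**Effect of a dose requirement on a patient who follows the schedule.** Week 8 is Day 56 (Protocol Table 6-1). The last blinded dose is taken that morning (Protocol 3.1); assume 06:00 to 10:00. Adding 36 hours gives 18:00 to 22:00 on Day 57. The phase starts after Day 56, that is, on Day 57. The shift in start date is 57 − 57 = 0 days. Only patients with a late or absent open-label dose, or no active blinded dose, are reclassified.

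**Illustration for the open-label summary, with every input assumed.** Let f be the share of patients in the phase with no open-label dose, and let p_s and p_n be the event rates in starters and non-starters. The reported rate is (1 − f)·p_s + f·p_n. Take f from 5% to 20%, which is 44 to 176 patients if all 882 entered the phase (882 × 0.05 = 44.1; 882 × 0.20 = 176.4).
- Drug-related event, p_s = 8%, p_n = 2%: 0.95 × 8 + 0.05 × 2 = 7.7%, falling to 0.80 × 8 + 0.20 × 2 = 6.8%. Relative to 8%, this is about 4% to 15% too low.
- Death, p_s = 2%, p_n = 6%: 0.95 × 2 + 0.05 × 6 = 2.2%, rising to 0.80 × 2 + 0.20 × 6 = 2.8%. Relative to 2%, this is 10% to 40% too high.

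The two examples move in opposite directions because of the rates chosen. They show why the direction cannot be stated.

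**The case against.** The strongest reply is that counting by period is deliberate. The SAP's Document History records the removal of on-treatment terminology and of the 28-day lag, and the change from treatment phase to study phase. Counting all FAS deaths by period ensures that none is lost, and safety has no inferential analysis (Protocol 9.5.3). This stands as an account of intent. It does not justify placing never-exposed patients in a group called pooled sacubitril/valsartan, where there is no randomized comparison to protect. A separate row also loses no deaths.

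Transparency is the second reply. SAP 2.3.1 reports premature discontinuation by phase, 2.4.1 reports exposure and dispensed dose levels, and all data are listed. A careful reader could see that some patients were off drug, but could not remove them from the counts. Patients who refuse visits and are followed by telephone will add few laboratory or vital-sign values; their deaths would still count.

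The third concerns the placebo doses. A reader might infer that the SAP overlooked them. It did not: 2.1.1 defines active-treatment assessments from the third dose in the sacubitril/valsartan arm, and 2.8.1.4 splits the adverse events of special interest at that point. Those provisions serve double-blind sensitivity analyses and do not take never-active patients out of the pooled phase.

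**Conclusion.** The point holds for deaths, notable laboratory values, notable vital signs and symptomatic hypotension in the open-label and pooled phases. For adverse events the text is ambiguous. It is a low-cost improvement to descriptive tables; its size and direction are unknown.

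Four stronger readings are not supported:
- **That all time off drug after Week 8 is miscounted.** The treatment-emergent rule has no end date, so events after a patient stops open-label drug stay in by design. The point concerns patients who never started.
- **That the adverse event tables are certainly affected.** The phase-specific first-dose dates leave another reading open.
- **That the added patients are on a non-study ACE inhibitor or ARB.** Protocol 5.5.6 permits this; nothing shows how often it happens.
- **That efficacy or the randomized safety comparison is biased.** The double-blind phase is separately defined and is not touched.

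The protocol also differs on who enters open-label treatment: all patients in the summary and in 3.1 and 5.1.2, but those completing 8 weeks of treatment in 5.5.4. That is a separate protocol matter and adds no weight here.

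**What to change.** Amend SAP 2.1.1 before database lock and apply the change to 2.8.1.2, 2.8.2, 2.8.3 and 2.8.4.2:
1. Limit the open-label summaries to patients with at least one recorded open-label dose, starting at the first open-label dose date that 2.1.1 already defines.
2. Limit the pooled summaries to patients with at least one active sacubitril/valsartan dose: the third blinded dose or later in that arm, or any open-label dose. This extends the active-treatment definition already in 2.1.1.
3. Report post-Week 8 events and deaths in patients with no open-label dose in a separate row by randomized arm. Events between Week 8 and a late first open-label dose should go in the same row, so that none drops out.

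For a patient with active blinded doses but no open-label dose, double-blind events stay in the pooled summary and post-Week 8 events go to the separate row. Leave the double-blind phase and its comparisons as they are. Events after a patient stops open-label drug remain counted.

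The cost is SAP wording, one dosing flag and extra table rows. The open-label dose date is on the Visit 7 form, and third-dose status is already summarized with the discharge data (SAP 2.3.3). No protocol amendment, visit or test is needed.
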